12	Appendices
Appendix I:	Contraception
Appendix II:	Signature Pages and Responsible Persons for the Study40
Signature Pa	ge –Protocol Lead

Signature Page – Coordinating Investigator	42
CCI	43
Appendix IV: Prohibited Medication, Food and Activities During the Study	50
Appendix V: Protocol Amendment History	52

Table of In-Text Tables

Table 1	Schedule of Assessments for Participants Transitioned from Part
	A1: Single Agent Therapy once weekly11
Table 2	Laboratory Assessments

Table of In-Text Figures

Figure 1 Study design diagram of ATR inhibitor Transition Rollover Study...14

List of Abbreviations

AE	Adverse event
ATM	Ataxia telangiectasia mutated
ATR	Ataxia telangiectasia mutated and Rad3-related protein
ATRi	Ataxia telangiectasia mutated and Rad3-related protein inhibitor
СҮР	Cytochrome P450
eCRF	Electronic Case Report Form
EDC	Electronic data capture
NCI-CTCAE	National Cancer Institute Common Terminology Criteria for Adverse Events
DDR	DNA damage response
FSH	Follicle-stimulating hormone
GCP	Good Clinical Practice
HRT	Hormone replacement therapy
IB	Investigator's Brochure
ICF	Informed Consent Form
ICH	International Council for Harmonisation
IEC	Independent Ethics Committee
IR	Ionizing radiation
IRB	Institutional Review Board
MedDRA	Medical Dictionary for Regulatory Activities
SAE	Serious adverse event
TEAE	Treatment-emergent adverse event

1 Synopsis

Clinical Study Protocol Number	MS20193-0007
Title	A Rollover Study to Provide Continued Treatment with M6620
Study Phase	Ι
IND Number	Not applicable
FDA covered study	No
EudraCT Number	2017-002354-37
Coordinating Investigator	PPD
Sponsor	Merck KGaA [name]
Study sites/countries	The number and nature of the study sites will be determined by the actual need. At the time of initiation of this protocol, it is expected that participants from a single site in the UK will enter this Safety Follow Up study.
Planned study period (first participant in-last participant out)	Estimated 5 years
Trial Registry	EudraCT

Objective:

Primary Objective:

• To monitor the safety of participants who are on long-term treatment with M6620 (berzosertib).

Methodology: This clinical study enables further treatment with M6620 (referred to as berzosertib henceforth) and safety follow up of participants from Vertex clinical study VX13-970-002, that was terminated. Therefore, this is a multicohort study not requiring any study committees. Participants enrolled in the Merck KGaA-sponsored rollover study will continue treatment with berzosertib on the same dose and schedule as the original study. Participants receiving combinations of berzosertib with other drugs in the study from which the participant is transitioned will continue to receive the same combination drugs in this Safety Follow Up study. Combination drugs will be obtained from the local study site pharmacy. The participants will complete a Safety Follow Up visit to be scheduled 28 (+7) days after the last administration of berzosertib.

Document No. CC Object No. CC	C O N F I D E N T I A L I N F O R M A T I O N	9/54
	Global Version ID: CC	

Planned number of participants: This is a rollover study to allow the participants to continue their treatment. Therefore no sample size considerations were undertaken.

Primary endpoints: Occurrence of adverse events (AEs) and treatment-related AEs in participants receiving berzosertib, graded according to the National Cancer Institute Common Terminology Criteria for AEs (NCI-CTCAE) (Version 4.03).

Secondary endpoints: Not applicable.

Pharmacokinetics: Not applicable.

Diagnosis and key inclusion and exclusion criteria: Participants on ongoing treatment with berzosertib either as monotherapy or in combination with other drugs at the time of transitioning will be enrolled in this study.

Study Intervention: dose/mode of administration/dosing schedule:

Berzosertib CCI mode of administration: intravenous infusion after dilution in CCI before intravenous infusion.

Dosage and schedule will be diverse, depending on the details of treatment in the study from which the participant transitioned. Participants will continue receiving treatment at the same dosage and according to the same schedule from which the participant transitioned.

Reference therapy: dose/mode of administration/dosing schedule: Not applicable.

Planned study and treatment duration per participant: Participants can continue treatment until disease progression or unacceptable toxicity is reported. The End of Study is defined by the completion of a Safety Follow Up visit to be scheduled 28 (+7) days after the last administration of berzosertib.

Statistical methods:

CCI

Safety:

All safety data summaries will be based on the safety analysis set.

Adverse events will be coded according to the latest available version of the Medical Dictionary for Regulatory Activities (MedDRA). Severity of AEs will be graded using the NCI-CTCAE (Version 4.03) toxicity grades. Adverse events will be summarized by frequency and incidence using MedDRA.

Safety data measurements will be summarized by dose group and/or time point using descriptive statistics for observed values and change from baseline values (as appropriate).

Table 1Schedule of Assessments for Participants Transitioned from Part A1: Single Agent Therapy once weekly

		Treatment Cycle (21 days)		Follow Up ^b	
Event/Assessment ^a	Enrollment	Day 1	Day 8	Day 15	28 (+7) days after last administration
Safety Assessment					
Informed consent	Х				
Demographic and other Baseline Characteristics	Х				
Concomitant medication/AEs	Continuous from signing Informed Consent Form through Safety Follow Up visit				
Study Intervention Administration					
Berzosertib dosing		Х	Х	Х	

AE = Adverse event

a Physical examination, weight, vital signs, serum chemistry, hematology and urinalysis will be measured as per Standard of Care and institutional guidelines and as clinically indicated; only clinically significant values should be reported as AEs.

b Follow Up will include a Safety Follow Up Visit to be scheduled 28 (+7) days following the last administration of berzosertib.

Document No.	CCI
Object No CC	

Global Version ID: CCI

2 Sponsor, Investigators and Study Administrative Structure

This clinical study will be sponsored by Merck KGaA (Darmstadt, Germany).

The number and nature of study sites will be determined by the actual need. It is expected that participants from a single site in the UK will enter this Safety Follow Up study. Further sites and countries may be added via amendment(s) to this protocol in the future if new demand for participants transitioning into this transition rollover study emerges.

The Coordinating Investigator will provide expert medical input and advice relating to study design and execution and is responsible for the review and signoff of the clinical study report.

Signature pages for the Medical Responsible and Coordinating Investigator are in Appendix II.

The study will appear 12 months after the last clinical visit of the final study participant, or another appropriate date to meet applicable requirements, in the following clinical trial registry: EudraCT.

Details of structures and associated procedures will be defined in a separate Manual of Operations, which will be prepared under the supervision of the Clinical Study Leader.

3 Background Information

Chemotherapeutic agents and ionizing radiation that induce DNA damage are an effective and common treatment option for patients with many types of solid tumors. However, many cancers, despite displaying initial sensitivity and clinical response to these agents, ultimately progress. One mechanism that has been proposed to protect tumor cells from DNA damage is the DNA damage response (DDR) pathway regulated by the kinases ataxia telangiectasia mutated (ATM) and ataxia telangiectasia mutated and Rad3-related protein (ATR). In many malignant cells, ATR assumes a crucial role in protecting cancer cells from DNA damage and from subsequent cell death after chemotherapy and ionizing radiation (IR). A reliance on ATR can arise from expression of oncogenes that drive deregulated proliferation and high levels of replicative stress or from defects in ATM/p53 signaling. Thus, small molecule-mediated inhibition of ATR should enhance the effect of IR and DNA damaging chemotherapy on cancer cells.

Vertex Inc (Boston, MA, USA) developed a selective inhibitor of ATR protein (Vertex code VX-970). Merck KGaA acquired the rights for this compound and will continue the development. The Vertex study intervention, VX-970, will be referred to as berzosertib when used in this and future clinical studies.

Berzosertib is a potent, selective first-in class inhibitor of ATR. Inhibition of ATR enhances the cytotoxic effect of DNA damaging drugs and IR in several cancer cell line derived xenografts and primary patient-derived tumors xenografts. In contrast, normal cells seem to tolerate ATR inhibition since they can activate compensatory DDR signaling via the ATM/p53 pathway. In xenograft models, berzosertib markedly enhances the anticancer activity of numerous DNA damaging drugs and IR, often substantially delaying or completely halting tumor progression and promoting tumor regression.

Document No. CC	C O N F I D E N T I A L I N F O R M A T I O N	12/54	
	Global Version ID: CCI		

Consistent with the compensatory role of the ATM/p53 pathway in response to ATR inhibition in normal cells, defects in this pathway result in increased cell sensitivity to ATR inhibition. In isogenic cell studies it has been shown that loss of ATM or of its principal substrate p53, can markedly increase cell sensitivity to ATR inhibition. Similarly, in a large panel of 119 genetically diverse cancer cell lines, TP53 mutational status was shown to correlate with response to ATR inhibition in combination with DNA damaging agents.

In nonclinical experiments, ATR inhibition by berzosertib has been shown to enhance the anticancer effects of DNA damaging agents, such as cisplatin and gemcitabine, and has been shown to exhibit activity as a single agent in a limited set of tumor lines.

Study VX13-970-002 was a Phase I clinical study initiated by Vertex studying berzosertib. For the initial dose escalation period (Parts A1, A2, B1, and B2), eligible participants had advanced stage solid tumors that have progressed through at least 1 line of therapy and had no approved treatment options. Early signs of clinical efficacy were observed in participants receiving berzosertib in the Vertex clinical study VX13-970-002. At the time of VX13-970-002 study completion, there was a participant from Part A1 still receiving treatment. This participant transferred to Study MS201923-0007 to continue receiving berzosertib.

Refer to the current berzosertib Investigator's Brochure (IB) for further information about the nonclinical and clinical programs and Guidance for the Investigator.

These clinical studies were conducted in compliance with the clinical study protocol and International Council for Harmonisation (ICH) Good Clinical Practice (GCP; hereafter referred to as ICH GCP) and any additional applicable regulatory requirements.

3.1 Study Rationale

This study is designed to provide continuous access to treatment with berzosertib for eligible participants from Vertex clinical study VX13-970-002 (parent study), and to collect long-term safety data. Additional participants may be added via amendment(s) to this protocol in the future if new demand for participants transitioning into this rollover study emerges.

4 Study Objectives

4.1 **Primary Objective**

• To monitor safety of participants that are on long-term treatment with berzosertib.

4.2 Secondary Objectives

None.

Document No. CC	C O N F I D E N T I A L I N F O R M A T I O N	13/54
	Global Version ID: CCI	

5 Investigational Plan

5.1 Overall Study Design and Plan

Participants from the Vertex clinical study VX13-970-002 still on active berzosertib treatment at the time of termination/transition may be enrolled in the Merck KGaA-sponsored study and continue treatment with berzosertib as monotherapy or in combination with other drugs and be monitored for safety. A schematic of the study design is presented in Figure 1. A schedule of study procedures/assessments is provided in Table 1.

Figure 1Study design diagram of ATR inhibitor Transition Rollover Study

Participants enrolled in the Merck KGaA-sponsored rollover study will continue treatment on the same dose and schedule as the original study, and will be monitored for safety as specified in Table 1. The participants will complete a Safety Follow Up visit to be scheduled 28 (+7) days after the last administration of berzosertib. Participants who transferred from combination treatment to berzosertib monotherapy before enrollment in this study should continue accordingly.

5.2 Discussion of Study Design

This will be a multicohort Safety Follow Up study. Participants will be transitioned from Vertex clinical study VX13-970-002. The participants will continue treatment on the same dose and schedule as the original study after being transitioned. The number and nature of the cohorts will be determined by the treatments in the studies from which participants are transitioning.

5.2.1 Scientific Rationale for the Study Design

To continue treatment and monitoring of safety of participants who are on treatment with berzosertib in a study at the time when that study is to be terminated.

5.2.2 Justification for Dose

Participants in this rollover study will continue to receive the dosage of berzosertib and any other study intervention(s) that are being used in the study from which they transitioned. In case of a dose/schedule modification in the previous study, participants will continue on the modified dose/schedule.

5.2.3 Rationale for Endpoints

This will be a study to monitor the safety of participants who are on long-term treatment receiving berzosertib either as monotherapy or combination treatment. Therefore, no other endpoints beyond safety monitoring are required.

5.2.4 Inclusion of Special Populations

Not applicable.

5.3 Selection of Study Population

Only participants that are ongoing with treatment in the Vertex study VX13-970-002 may be enrolled into this study. Participants will be transitioned from the VX13-970-002 study to enable them to continue treatment with berzosertib. Prior to performing any study assessments not part of the participant's routine medical care, the Investigator will ensure that the participant or the participant's legal representative has provided written informed consent following the procedure described in Section 9.2.

Document No. CCI	C O N F I D E N T I A L I N F O R M A T I O N	15/54	
	Global Version ID: CCI		

M6620

MS201923-0007

- Ongoing treatment in Vertex clinical study VX13-970-002 (parent study)
- Participant must be able to understand and provide written informed consent
- Participant must be willing and able to comply with the scheduled visits, treatment plan, lifestyle, laboratory tests, contraceptive guidelines (as described in Appendix I), and other study procedures.

5.3.2 Exclusion Criteria

• Participants experiencing disease progression or unacceptable toxicity at the time of transition from the VX13-970-002 study into the Safety Follow Up study.

5.4 Criteria for Initiation of Study Treatment

Participants will continue the treatment with berzosertib as monotherapy or in combination with other study interventions as administered in the VX13-970-002 study.

5.5 Criteria for Participant Withdrawal

5.5.1 Withdrawal from Study Therapy

A participant must be withdrawn from study treatment if any of the following occur in this Safety Follow Up study:

- Participant withdraws consent
- Participant is reported to have disease progression or unacceptable toxicity
- Participation in another clinical study
- Any events that unacceptably endanger the safety of the participant
- Protocol noncompliance (to be discussed on a case-by-case basis with the Sponsor).

5.5.2 Withdrawal from the Study

Participants may withdraw from the study at any time without giving a reason. Withdrawal of consent will be considered withdrawal from the study.

A participant must be withdrawn if any of the following occur during the study:

- Participant withdraws consent
- Participant is lost to follow up
- Participation in another clinical study.

Document No. CC	C O N F I D E N T I A L I N F O R M A T I O N	16/54
	Global Version ID: CCI	

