7.4.1.3 Definition of the Adverse Event Reporting Period

The AE reporting period for safety surveillance begins when the participant is initially enrolled in the study (date of first signature of informed consent/date of first signature of first informed consent) and continues until 28 days after the last administration of berzosertib.

Any SAE assessed as related to berzosertib must be reported whenever it occurs, irrespective of the time elapsed since the last administration of berzosertib.

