7.4.1.6 Monitoring of Participants with Adverse Events

Adverse events are recorded and assessed continuously throughout the study (see Section 7.4.1.3) and are assessed for final outcome at Safety Follow Up visit to be scheduled 28 (+7) days after the last administration of berzosertib. All SAEs ongoing at the Safety Follow Up visit must be monitored and followed up by the Investigator until stabilization or until the outcome is known, unless the participant is documented as "lost to follow up". Reasonable attempts to obtain this

Document No. CC	C O N F I D E N T I A L I N F O R M A T I O N	28/54	
	Global Version ID: CCI		

information must be made and documented. It is also the responsibility of the Investigator to ensure that any necessary additional therapeutic measures and follow up procedures are performed.

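### Protocol 5.5.2 requires exit from the whole study on joining another trial, which conflicts with the safety follow-up required to 28 (+7) days after the last dose

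*Protocol*

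**What the plan says.** Protocol 5.5.1 (withdrawal from study therapy) and 5.5.2 (withdrawal from the study) are separate lists, and both contain "Participation in another clinical study". The list in 5.5.2 is mandatory: "A participant must be withdrawn if any of the following occur during the study". Its other two entries are withdrawn consent and loss to follow up. It sets no timing condition and does not mention the post-dose period.

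The safety sections are tied to the last dose or to the follow-up visit:

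- **5.1:** "The participants will complete a Safety Follow Up visit to be scheduled 28 (+7) days after the last administration of berzosertib".
- **7.4.1.3:** the AE reporting period starts at consent and "continues until 28 days after the last administration of berzosertib". An SAE assessed as related to berzosertib "must be reported whenever it occurs, irrespective of the time elapsed since the last administration of berzosertib".
- **7.4.1.6:** AEs are assessed for final outcome at the Safety Follow Up visit. SAEs still open at that visit are followed further, "unless the participant is documented as" lost to follow up.
- **8.5.2:** treatment-emergent AEs are counted from consent to that visit, and AEs unresolved at the visit have their own listing.
- **5.7:** the study ends when the last participant has completed that visit.

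The SAP (Section 5) ties the only endpoint, occurrence of AEs, to 28 days after the last administration. SAP Section 7 says that data will be presented in listings only.

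**The concern.** Because 5.5.1 already stops treatment when another trial is joined, the entry in 5.5.2 can only add an end to study participation. For a participant who has stopped berzosertib but has not reached the Safety Follow Up visit, that means leaving the study while AE reporting and outcome assessment are still due.

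The other two entries in 5.5.2 describe people who have refused further participation or cannot be reached. Someone who joins another trial may be both reachable and willing, so here the rule itself would create the gap in the data.

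AE occurrence is the only endpoint, so no other endpoint offsets a gap in the post-dose period. The situation is plausible. Protocol Section 3 describes the parent study's dose-escalation participants as having advanced solid tumors and no approved treatment options, and treatment here ends at progression or unacceptable toxicity. The documents give no rate of entry into other trials.

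**Working it through.** The documents give no sample size, error rate or event figure to reproduce for this point. The check sets the passages side by side, with one line of arithmetic.

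**Step 1. Does each safety requirement allow for this exit?**

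| Protocol section | Requirement | Exception for joining another study? |
|---|---|---|
| 5.1 | Safety Follow Up visit, day 28 to day 35 after last dose | None |
| 7.4.1.3 | AE reporting to day 28 after last dose | None |
| 7.4.1.6 | Final outcome assessed at the visit; open SAEs followed afterwards | None (loss to follow up only) |
| 8.5.2 | Treatment-emergent AEs counted up to the visit | None |
| 5.7 | End of study set by the last participant's visit | None |

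**Step 2. Is there a bridging rule?** No section provides an early-withdrawal visit or general AE collection after study withdrawal. Section 7.4.2 expressly continues follow-up after withdrawal, but only for pregnancies. That contrast makes it reasonable to read 5.5.2 as ending other follow-up.

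**Step 3. What is lost on the literal reading, if another study is joined before the visit?**

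- *Lost:* new non-serious AEs, new SAEs judged unrelated, outcomes of AEs still open at exit, and the visit. Follow-up of open SAEs under 7.4.1.6 also loses its starting point, because it is defined for SAEs ongoing at the visit.
- *Not lost:* berzosertib-related SAEs, reportable without time limit (7.4.1.3), and AEs resolved before exit, whose outcomes are entered on an ongoing basis (7.4.1.2).
- *Undefined:* if the last participant leaves this way, the end-of-study event in 5.7 never occurs as worded.

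**Step 4. How much of the window?** Let d be the day after the last dose on which collection stops. Days lost = 28 − d, and share lost = (28 − d)/28. The values of d are assumptions, because the documents give none.

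| d | Days lost | Share of 28-day window | Visit lost? |
|---|---|---|---|
| 0 | 28 | 28/28 = 100% | Yes |
| 7 | 21 | 21/28 = 75% | Yes |
| 14 | 14 | 14/28 = 50% | Yes |
| 21 | 7 | 7/28 = 25% | Yes |
| 28, visit not yet held | 0 | 0/28 = 0% | Yes |
| After the visit | 0 | 0% | No |

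**Step 5. How many people?** The rationale for Amendment 2 (Protocol Appendix V) reports one participant enrolled to date. One such exit would therefore affect the post-dose data of every participant reported so far.

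**The case against.** The strongest reply is that 5.5.2 does not say in words that AE collection stops. Section 7.4.1.3 counts from the last dose, not from enrolment status, and 7.4.1.6 excuses only loss to follow up. A site could fairly treat these specific safety sections as still binding after exit. This stands as a possible reading. However, the pregnancy-only wording in 7.4.2 points the other way, and the text does not settle which section prevails. That is a reason to reconcile the passages.

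Three stronger conclusions are tempting, and the documents do not support them:

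- A reader might infer that all SAE information is cut off. It is not, because related SAEs remain reportable at any time.
- A reader might infer that every final outcome in the study would be lost. Outcomes of AEs resolved before exit are already recorded, so only those still open are at risk.
- A reader might infer informative truncation that biases the primary endpoint. With one participant reported and no statistical analysis planned (SAP Section 7), there is no estimate to bias. The link between joining another trial and progression or toxicity is plausible, but the documents do not state it.

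It is also fair to say that the percentages above only restate the assumed days, and that nothing is lost if the other study starts after the visit. Both points stand. They limit the size of the problem without removing the contradiction.

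**Conclusion.** The contradiction is real and worth correcting. A mandatory exit rule in 5.5.2 has no exception for the post-dose period, while four other sections (7.4.1.3, 7.4.1.6, 8.5.2 and 5.7) rely on data or a visit after the last dose and do not allow for that exit.

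The effect is conditional. It needs entry into another study before the Safety Follow Up visit, and a site that reads withdrawal from the study as ending AE collection. Under those two assumptions the loss runs from the visit alone up to the visit plus the whole 28-day window. The practical consequence is an incomplete safety listing. It matters despite the small number because that listing is the study's only output on its only endpoint.

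**What to change.** Reconcile 5.5.2 with 7.4.1.3, 7.4.1.6, 8.5.2 and 5.7 in one of two ways:

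1. Delete the other-study entry from 5.5.2.
2. Keep it, and add a sentence saying that, subject to the participant's consent, AE and SAE collection and the Safety Follow Up visit continue to 28 (+7) days after the last berzosertib dose even if another study is entered.

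Both concern data collection only and leave 5.5.1 unchanged. Withdrawal of consent stays a separate reason for exit.

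In the AE listing (SAP 15.1), mark events with onset on or after the start of a new treatment, so that readers can separate the periods with and without it. Protocol 6.4 already has concomitant medications recorded with their duration and indication, and Table 1 continues this to the Safety Follow Up visit. The start date should come from those records, without a new data field.

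The cost is one protocol sentence and a minor SAP change. SAP Section 9 says that data are listed as collected with no derived datasets, so the mark needs a short exception there, or the start date can simply be shown beside AE onset. The remaining downside is that events after a new treatment starts are harder to attribute. The mark makes this visible but does not resolve it.
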